The second study is a randomized control trial of YLWH initiating ART to determine the effect of the CFLU mHealth tool on ART adherence. A total of 206 YLWH will be randomized to either Standard of Care (SoC) or CFLU plus SoC. Through the CFLU mHealth tool, participants will interact with a computer through IVR. Participants in the intervention arm will receive pill reminders, clinic visit reminders, health tips messages and functionality to support self-reported symptoms in addition to standard of care. During this second part of the research, youths will be assessed on knowledge of COVID-19 at baseline only.

The third study is nested within the randomized control trial and will assess the cost of the CFLU intervention when compared to SoC.

Conclusion

This project will determine acceptability, effectiveness, knowledge of COVID-19 and cost of delivering pill and clinic visit reminders, and messages on health tips to a population with suboptimal ART adherence. Results from this research will provide valuable insights into mHealth adherence interventions for YLWH and knowledge of COVID-19 in resource-limited settings.

CHAPTER ONE: INTRODUCTION

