3.3 Study population

The study population will comprise of YLWH aged 15 -24 years who are ART naïve or on ART since Jun 2019.

Target population:

Youth living with HIV registered to receive ART at any of the 3 ART clinic in Kiryandongo district :Kiryandongo Hospital, Panyandoli HCIII and Nyakadoti HCII

Accessible population:

[figure not shown]
Youths consented/assented for CFLU, registered for care at Kiryandongo hospital, Panyadoli HCIII or Nyakadoti CII.

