To assess effect of mHealth tool (CFLU) on ART adherence and knowledge of COVID-19 among YLWH naïve, initiating ART or on ART since Jun 2019.

RESEARCH & ETHICS COMMITTEE
[name]

Study design: Randomized control trial with 2 arms (Standard of Care or CFLU with Standard of Care)

Study purpose: To assess effect of CFLU on ART adherence among youth measured by interactive voice response to daily adherence calls mapped in the database and proportion with viral suppression of copies below 1000 copies/mL.

The intervention (CFLU) uses IVR calls or text messages delivered via MOTECH™ based Connect for Life technology™. The calls are delivered in 3 languages (Luganda, English and Runyakitara) and the participant has to make a choice of the preferred language during registration to the system. The system offers adherence pill reminders, health message tips, visit appointment reminders and receipt of self-reported symptoms.

A poor understanding of the disease among youths can result in delayed identification and treatment leading to rapid spread of infections among the community.

Study setting: Kiryandongo District, 3 sites offering HIV-ART. Kiryandongo hospital, Panyandoli Health Centre III and Nyakadote Health Centre II have been chosen as the study sites, the hospital has 1,322 YLWH and a viral suppression rate of 79% (Table 1). In 2018, a total of 637 YLWH were enrolled in care. By Jun 2019 and additional 218 YLWH had been enrolled in care. The current total at the site for age between 15-24 is 1,322. Overall retention was 79%. We have included the lower level health facilities since ART delivery is done majorly in these grassroot levels.

Study Population: Inclusion: YLWH (15-24 years), ART naïve or initiating ART since Jun 2019.

Exclusion: Hearing loss, severe illness likely to shorten life span, boarding school YLWH, Inability to use a basic mobile phone.

Sample size calculation:

Sample Size: X-Sectional, Cohort, & Randomized Clinical Trials (Kelsey et al., Methods in Observational Epidemiology 2nd Edition, Table 12-15; Fleiss, Statistical Methods for Rates and Proportions, formulas 3.18 & 3.19)

The sample size formula for the method described in Kelsey et. al. is:

$$n_1 = \frac{(Z_{\alpha/2} + Z_{1-\beta})^2 \bar{p} \bar{q} (r+1)}{r(p_1 - p_2)^2}$$

[figure not shown]
and

$$n_2 = rn_1$$

where

n_1 = number of cases in the intervention

n_2 = number of controls

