The Adult Care and Treatment Package includes the following services:(U. MoH, September 2014)

1. HIV counseling and testing
2. HIV prevention services
3. Nutritional Counseling and support
4. Opportunistic infection screening and management
5. Screening and management of non-communicable diseases
6. Diagnostics and laboratory monitoring
7. Sexual and reproductive health
8. Counseling and Psychosocial support
9. ARV preparation, initiation and monitoring
10. Adherence and retention into care
11. Palliative care
12. Mental health

[figure not shown]
[figure not shown]

Fig 5: Study Schema

The outcome variables include:

- ART adherence scores at 6 and 12 months, as assessed by HIV Care Card for those on SoC arm and Self- reported adherence to ART as depicted on the mHealth dash board.
- Viral load suppression at 6 and 12 months, as test results from blood collected at months 6 and 12 with time to viral suppression.
- Retention rates at 6 and 12 months with time to loss to follow-up
- Stigma scores at study start and end

Data Management Analysis Plan

Data collected on paper CRF will be entered using Research Electronic Data Capture software (REDCap) which is a safe, secure, HIPAA-compliant, web-based application and facilitates offline and online data entry. Data will be exported to STATA 14.0, for analysis. Data will then be backed up and archived in both soft and hard copy to avoid losses. The data collected will be stored securely under lock and key to maintain patient confidentiality.

Data regarding call details in the system will be extracted from CFL tool database, exported into Stata for analysis.

[figure not shown]
Visit dates will be extracted from database and proportions lost to follow-up drawn and time to loss to follow-up estimated. Viral load results will be extracted and time to viral suppression with survival analysis curves drawn for both arms.

Data from the MoH HIV card regarding the ART regimen and start dates will be transcribed to the data collection tool and later entered on the REDCap system.

General data analysis

Data will be analyzed at three levels, first at the univariate level, then at the bivariate level and lastly at the multivariate level. A consort diagram will be drawn to show the screening, enrolment, randomization, follow-up and analysis flow of the study.

Univariate Analysis

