7. Date of Birth ____/____/____ 1995	8. Gender  Male  Female	9. Ethnicity (Tribe) _____																			

Section C: Social Assessment

11. Known HIV test results?

- Positive
- Negative.

12a) Previous VL test results (N/A if initiating ART)

--	--	--	--	--	--

12b) Date of test results

13. Do you have a partner?

No(if no, go to 14)
 Yes

13 a. If Yes, for how long have you been with your partner

(Yrs., Months)

11a. If positive are you receiving ART treatment?

Yes
 No

11b. If yes, list ART start dates

J. J. —

DD/MM/YYYY

11c: ART Regimen: (Use MoH Codes)

[figure not shown]
--	--	--

14. Have you shared your test results with any
one? Yes No

14. If yes, with who? List relationship

[figure not shown]
a) -----

b) -----

Section D: Education Living Standards

1. Highest level of Schooling Completed
 
 No Formal Education.
 
 P1-P4
 
 P5-P7
 
 S1-S4.
 
 S5-S6
 
 Technical/ University
	
2. Are you currently working?
 
 Yes  No
 
2a. If yes what is your current occupation?

3. What is your household income /month?
 
(Consider ALL sources of income, self or guardian)
 
 Less than 50,000
 
 50,000/= and 100,000
 
 100,001/= and 500,000
 
 500,001/= and 1,000,000
 
 Above 1,000,000
 
 Declined to answer
	
4. Number of people supported on income?
 
 

5. Number of Children  <18 in household (# each age)
 
1. 0-4 Years 
 
2. 5-9 Years 
 
3. 10-14 Years 
 
4. 15 –18year 
	
6. Housing Description
 
 Mud floor walls with no ventilation
 
 Mud floor brick walls with one small window
 
 Brick house with enough windows
 
 Brick house with enough glass windows and well ventilated
 
 Other(Camp, Unipot etc)

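### Time-to-suppression curves have no at-risk rule although youth already on ART can enter, and baseline suppression is not a named covariate (minor)

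*Combined protocol and SAP*

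**What the plan says.** All references are to the combined protocol and SAP. Under Objective 2 (section 3.4), the outcome list defines viral suppression "as test results from blood collected at months 6 and 12 with time to viral suppression". The Data Management Analysis Plan adds: "Viral load results will be extracted and time to viral suppression with survival analysis curves drawn for both arms". The definitions page sets suppression at below 1000 copies/mL. Viral load is drawn at baseline and at the 6- and 12-month visits (days 168 and 336, each ±14).

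The documents differ on who enters:

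- Abstract, Methods: "The second study is a randomized control trial of YLWH initiating ART".
- Section 3.3: "The study population will comprise of YLWH aged 15 -24 years who are ART naïve or on ART since Jun 2019".
- Objective 2 statement: "among YLWH naïve, initiating ART or on ART since Jun 2019".
- Objective 2 entry criteria: "Inclusion: YLWH (15-24 years), ART naïve or initiating ART since Jun 2019" and "Exclusion: Hearing loss, severe illness likely to shorten life span, boarding school YLWH, Inability to use a basic mobile phone".

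None of these lines sets a viral-load limit. Section C of the demographic and medical evaluation form has a field for "Previous VL test results (N/A if initiating ART"), so participants with treatment history are expected.

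The Bivariate Analysis paragraph names age, gender, ART duration, marital status, education, occupation and religion as independent variables. Other variables reach the multivariable model by p ≤ 0.05 screening or by being judged scientifically relevant. Baseline viral load is not named.

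**The concern.** A time-to-event curve needs an at-risk set, a time origin and an event rule, and the plan states none of them. A youth who enters suppressed cannot become suppressed for the first time after randomisation. An analyst could drop such youth, count them as events at time zero, or count them at month 6 if still suppressed. These choices give different curves, and the last two do not show how fast viraemic youth become suppressed. With two post-baseline samples, a curve that treats visit dates as event dates also implies a precision that the data lack.

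Baseline suppression is an obvious prognostic factor for suppression at months 6 and 12. If its entry into the model is decided after the data are seen, the adjusted arm effect depends on an avoidable choice.

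**Working it through.** **The plan's own figure.** For 79% v 94%, two-sided 5% and 80% power, the Kelsey formula gives (1.960 + 0.842)² × 0.865 × 0.135 × 2 / 0.15² = 81.5 per arm (stated 81). Fleiss gives 81 (stated 80), or 94 with continuity correction (stated 93). Then 186 / 0.9 = 206.7 (stated 206). The sample size reproduces to within about one per arm and is not in question.

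**How many may be suppressed at entry.** The share on ART, f, is not given; I assume 25 to 75% and take ART-naive youth as not suppressed. Among those on ART I use the hospital's 79% (section 3.2 and Table 1, December 2018; 80%, or 208/260, in June 2019). As a low value I use 55.3%, a regional rate for all adults (Fig 6). The share suppressed at entry is s = f × rate.

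| f | Rate | s | Suppressed, of 206 | 1 − s | Viraemic, of 186 evaluable |
|---|---|---|---|---|---|
| 25% | 55.3% | 0.138 | 28.5 | 0.862 | 160 |
| 50% | 55.3% | 0.277 | 57.0 | 0.724 | 135 |
| 75% | 55.3% | 0.415 | 85.4 | 0.585 | 109 |
| 25% | 79% | 0.198 | 40.7 | 0.803 | 149 |
| 50% | 79% | 0.395 | 81.4 | 0.605 | 113 |
| 75% | 79% | 0.593 | 122.1 | 0.408 | 76 |

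**What the curve would show, by event rule.** Let v be the month-12 proportion suppressed among viraemic entrants.

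- Rule A, baseline suppression counts as an event: the curve ends at s + (1 − s)v. The arm difference is therefore (1 − s) times the difference among viraemic youth.
- Rule B, only month-6 and month-12 samples count: if ever suppressed by month 12 is taken as suppressed at month 12, the curves end at the whole-trial proportions, 79% v 94%. The (1 − s) shrinkage does not arise, but maintained and achieved suppression are still pooled.

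**Illustration of rule A.** Take 79% v 94% as whole-trial results, a common odds ratio in both baseline groups, s = 0.395 and an assumed control-arm gap of 0.20 between those groups. Control: v = 0.79 − 0.395 × 0.20 = 0.711. Solving for the odds ratio that gives 94% overall puts v at 0.915 in the CFLU arm, a difference of 20.4 points. The unrestricted curves end at 0.395 + 0.605 × 0.711 = 0.825 and 0.395 + 0.605 × 0.915 = 0.949, which is 12.3 points apart. Over gaps of 0.05 to 0.30 (where feasible) and all s above, the viraemic difference is 15.5 to 27.0 points and the unrestricted difference 6.9 to 14.6. Expected month-12 failures are 93 × 0.21 + 93 × 0.06 = 25.1. About 1 to 13 of them would be rebounds that rule A counts as suppressed.

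**Value of adjusting.** I simulated 60,000 trials per scenario with 93 per arm, comparing the unadjusted chi-square test (power about 87.5%) with a Mantel-Haenszel test stratified by baseline suppression. Power changes by −0.3 to +0.9 points for gaps of 0.05 to 0.20, and by about +2 points for a gap of 0.30.

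**The case against.** A reader might infer that the planned curve counts a youth who enters suppressed and later rebounds as a success, and that it dilutes the arm difference to 41 to 86% of its size. The documents do not support that reading. They tie the outcome to month-6 and month-12 blood and do not say that baseline suppression is an event. The rule A figures depend on a rule that the plan does not contain, on an unknown share on ART and on an assumed gap. Suppression at month 6 followed by rebound would count as an event in any first-suppression curve, including a restricted one.

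The time origin could also be ART start, since start dates and earlier viral loads are recorded; a first-suppression time is then conceivable for some youth on ART. That is possible, but it is not stated, and it would no longer be a time from randomisation.

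On the covariate, unadjusted randomised comparisons are valid, ART duration is listed and partly stands in for baseline status, and the power gain is small. All of that stands.

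A reader might also infer that allocation was not stratified by baseline suppression. This cannot be checked: the randomisation details referred to are not in the available text, and Fig 5 is not shown. The baseline blood draw is described after randomisation, so only an earlier clinic result could have been used.

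Finally, the Abstract's wording suggests initiators only. Section 3.3, the Objective 2 statement and the evaluation form say otherwise.

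**Conclusion.** The point holds as a gap in definition and is minor. The curves are promised for both arms with no at-risk set, time origin or event rule, while youth probably suppressed at entry can be enrolled. The times are known only to intervals of about six months. Roughly 28 to 122 of 206 could be affected, but only on the assumed 25 to 75% on ART and the borrowed suppression rates. Shrinkage of the arm difference and rebound counted as success follow only if baseline suppression is treated as an event.

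The covariate limb is confined to the analysis plan. Naming baseline suppression in advance protects against chance imbalance and data-driven model choice; it is not a power argument. The curves are secondary, no test on them is specified, and neither the unadjusted binary comparisons nor N = 206 is affected.

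**What to change.** 1. Restrict the time-to-suppression analysis to participants with baseline viral load of at least 1000 copies/mL. Use randomisation as time zero and a discrete-time or interval-censored method over the two visit intervals. Report maintained suppression at months 6 and 12 separately for those below 1000 at baseline. Leave participants with no baseline result out of the curve and report their number.
2. Pre-specify adjustment or stratification of the month-6 and month-12 arm comparisons by baseline suppression (below 1000 v at least 1000). Keep other covariates few, because only about 25 failures are expected at 79% v 94%.
3. Reconcile the wording on who is enrolled between the Abstract and the Objective 2 text.

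This is a change of wording only, since baseline viral load is already collected. The cost is a smaller curve: about 76 to 160 of 186 evaluable participants under the assumptions above. If a 79% v 94% difference held among viraemic youth, a two-proportion comparison confined to them would have power of about 77%, 65% or 48% at 25%, 50% or 75% on ART (79% rate). With all 93 per arm it would have about 86%. The restricted curve should therefore stay descriptive.

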Loss to follow-up: Missing 2 visits consecutively, not able to ascertain vitals

mHealth: use of mobile technology e.g. mobile phones and other wireless technology for health-related activities

Retention in care: Continuous engagement in clinical care for 1 year

Virological suppression: Viral load less than 1000 copies/ml

Youth Living with HIV/AIDS: Persons living with human immunodeficiency virus/ acquired immunodeficiency syndrome aged 15 to 24yrs (United Nations General Assembly Resolution A/RES/50/81 ("World Programme of Action for Youth to the Year 2000 and Beyond"))

LIST OF ABBREVIATIONS

AIDS: Acquired Immuno Deficiency Syndrome

cART: Combined Antiretroviral Therapy

CD4 cell: Cluster Differentiated cells

cDOT: Community based Directly Observed Treatment

CFLU: Call for Life Uganda

CITI: Collaborative Institutional Training Initiative

COVID-19: CORONA VIRUS DISEASE 2019

GCP: Good Clinical Practice

HIT: Health Information Technology

[figure not shown]
HIV RNA: Human Immunodeficiency Virus Ribonucleic Acid

HSP: Human Subjects Protection

IAC: Intensive Adherence Counselling

IDI: Infectious Diseases Institute

IVR: Interactive Voice Response

MoH: Ministry of Health

PEPFAR: President's Emergency Plan for AIDS Relief

PHS: Physical Health Scores

PLWH: People living with HIV

SMS: Short Messaging Service

[figure not shown]
UBOS: Uganda Bureau of Statistics

UNAIDS: United Nations Programme on HIV and AIDS

UPHIA: Uganda Population-Based HIV Impact Assessment

VL: Viral load

YLWH: Youth living with HIV

ABSTRACT

Version 3.2, 12th Jan 2022

Background:

An estimated 3.9 million[2.1–5.7 million] youth were living with HIV (YLWH) globally in 2017, most of whom live in sub-Saharan Africa (Avert.Org, 2019; UNAIDS, 2018b). Young people are the only population group in which AIDS-related deaths are increasing (UNAIDS, 2019a). AIDS is the leading cause of death among young people in sub-Saharan Africa (Avert.Org, 2019).

In Uganda, there were 160,000 YLWH in 2018 (UNAIDS, 2019b). An estimated 53,000 new HIV infections occurred among youth in 2018, accounting for 26% of HIV incidence in the country (Avert.Org, 2019).

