Ratio of sample size. Unexposed/Exposed:	1
Percent of Unexposed with Outcome:	79
Percent of Exposed with Outcome:	94
Odds Ratio:	4.2
Risk/Prevalence Ratio:	1.2
Risk/Prevalence difference:	15

	Kelsey	Fleiss	Fleiss with CC
Sample Size - Exposed	81	80	93
Sample Size-Noneexposed	81	80	93
Total sample size:	162	160	186

References

Kelsey et al., Methods in Observational Epidemiology 2nd Edition, Table 12-15
 Fleiss, Statistical Methods for Rates and Proportions, formulas 3.18 & 3.19
 CC = continuity correction
 Results are rounded up to the nearest integer.
 Print from the browser menu or select, copy, and paste to other programs.

Results from OpenEpi, Version 3, open source calculator--SSCohort
 Print from the browser with ctrl-P
 or select text to copy and paste to other programs.

MAKERERE UNIVERSITY
 SCHOOL OF MEDICINE
 RENEWAL
 VALID UNTIL

★ 10 FEB 2023 ★

RESEARCH & ETHICS COMMITTEE
 103 FOR EACH ARM, KAMPALA

Factoring 10% loss to follow-up, the total sample size will be 206(103 for each arm, KAMPALA)

[figure not shown]
Data collection procedures:

The intervention is mobile phone based IVR. However, the CLFU trial found that, it was observed that a good number of participants (50 of 256) at the urban site were not enrolled due to absence of a basic mobile phone, or had malfunctioning phone keyboards (for Poster Exhibition at the 20th International Conference on AIDS and STIs in Africa (ICASA 2019). Therefore, we shall provide a basic mobile phone to everyone in the study (SoC and intervention arm). To avoid stigma associated with a particular phone, we shall get 4 or more types of basic phones. Issues regarding simcard registration will be dealt with by the individuals.

Four study questionnaires will be administered at baseline and 6-monthly until the 12-month exit visit.

The questionnaires will capture:

- Sociodemographic and medical history
- Stigma scores
- Knowledge assessment
- Sexual behavior assessment
- Knowledge of COVID-19 (only at baseline)

The data will be entered using REDCap. Blood for viral load will be collected at baseline and at the 6 and 12-month visit.

Intervention: mHealth CFLU tool

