The study findings will be reported as odds ratios, confidence interval and independent variables found to have p value ≤ 0.05 at 95% confidence interval will be considered to be statistically significant in the final model.

[figure not shown]
After the final model, significant factors for ART adherence/ viral suppression will be computed.

Data Monitoring Committee:

The DMC will consist of 3 independent members with expertise in relevant clinical specialties, their responsibility is to ensure that the safety of study subjects is protected while the scientific goals of the study are being met. The previous CFL-RCT at IDI, had no major safety issues and neither were there any gender-based violence, so the DMC will suffice and will be involved in:

- Review the research protocol and plan for data safety and monitoring.

- Evaluate the progress of the trial, including periodic assessments of data quality and timeliness, participant recruitment, accrual and retention, participant risk versus benefit, performance of the trial site, and other factors that can affect study outcome.
- Make recommendations to the PI about continuation, termination, or other modifications of the trial based on the observed beneficial or adverse effects of the intervention under study.
- If appropriate, conduct interim analysis of efficacy in accordance
- Recommend solutions to address problems with study conduct, enrolment, and sample size and/or data collection.

Study visits (scheduled and unscheduled visit codes)

The total duration of the study is 18 months; follow up period is up to 12 months. The participant has a baseline visit (00.0) and is followed up at month 6 (168 days \pm 14 days) visit code 01.0, last visit is at month 12 (336 days \pm 14 days) visit code 02.0.

The participant might return at the clinic due to an illness, or repeat blood draw, this interim visit codes will be numbered sequentially from the previous scheduled visit. (00.01, 00.02 if its next to the baseline, if next to second visit, the code will be 01.01, 01.02 etc., if its next to last visit it will be coded 02.1, 02.2, etc.).

The study visit window is 2 weeks (14 days), beyond this period a visit code denoting an interim visit is given; e.g. Visit code 01.1 first contact with patient past visit 01.0 and 01.2 denotes second contact with patient past visit 01.0.

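### Time to viral suppression is planned as an ordinary survival outcome, but viral load is scheduled only at baseline, month 6 and month 12, and the plan names no event date or interval-censored method

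*Combined protocol and SAP*

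**What the plan says.** All places are in the combined protocol and SAP, section 3.4 (Study Objective 2) unless noted.

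- The outcome list has: "Viral load suppression at 6 and 12 months, as test results from blood collected at months 6 and 12 with time to viral suppression". The definitions at the front give the threshold: "Virological suppression: Viral load less than 1000 copies/ml".
- The Data Management Analysis Plan adds: "Viral load results will be extracted and time to viral suppression with survival analysis curves drawn for both arms". It names no event date, time origin, censoring rule, estimator or test for this outcome.
- Data collection procedures: "Blood for viral load will be collected at baseline and at the 6 and 12-month visit".
- Study visits puts the month 6 visit at day 168 and the month 12 visit at day 336, each ± 14 days. Later contacts are coded as interim visits. An interim visit may include a repeat blood draw; neither its trigger nor its frequency is given.
- Abstract, Methods: "Participants in the intervention arm will receive pill reminders, clinic visit reminders, health tips messages". Under Missed visit, dropped CFLU calls trigger active tracing. Physical tracing after two weeks is not restricted to one arm.

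**The concern.** An ordinary survival curve needs one date per event. Here the event is never seen to happen; a sample only shows that it has happened since the last sample. The one date attached to a scheduled result is the date of the draw. If that date is used, events form two clusters, near day 168 and day 336. The order of events within a cluster is the order in which people attended, and a participant who misses month 6 has the event moved to month 12.

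Both features are open to the intervention. Visit reminders and dropped-call tracing are meant to affect whether, and perhaps when, the measuring visit takes place. A difference in attendance could then be read as faster virological response, most plausibly in favour of CFLU.

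**Working it through.** **1. The plan's own figure.** The plan gives no event count, hazard ratio or power for time to suppression. Its sample size is for the binary comparison of 79% with 94%. By the printed Kelsey formula, with mean proportion 0.865: (1.960 + 0.842)² × 0.865 × 0.135 × 2 / 0.15² = 81.5 per arm (plan: 81). Fleiss with continuity correction gives 94 (plan: 93). Then 186 / 0.9 = 206.7 (plan: 206). The figure reproduces to rounding, and it does not depend on how suppression is dated.

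**2. What the samples can show.**
- Baseline to month 6: 168 ± 14, so 154 to 182 days.
- Month 6 to month 12: shortest (336 − 14) − (168 + 14) = 140 days, longest (336 + 14) − (168 − 14) = 196 days.
- Month 6 draw missed: 336 ± 14, so 322 to 350 days.

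The uncertainty in each event time is thus about 24 weeks, or about 48.

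**3. Visit timing (simulation).** Assumptions, none from the documents: 50 viraemic participants per arm; in both arms 75% suppressed by month 6 and half of the rest by month 12; visit day = 168 or 336 plus a Normal(4 − shift, SD) offset clipped to ± 14, where the shift applies to CFLU only; nobody misses a visit. Entries are rejection rates of a two-sided 5% log-rank test. Ranges cover repeat runs; single values are one run.

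| CFLU earlier by | Draw date, SD 5 | Draw date, SD 8 | Draw date, SD 10 |
|---|---|---|---|
| 2 days | 12–14% | 7–9% | 5–7% |
| 4 days | 34–41% | 17–21% | 13–15% |
| 6 days | 60–64% | 34% | 23–26% |

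With no shift the draw-date test rejects in about 4–6%. By nominal visit (6 or 12) it stays at about 5% (3–8% across runs). At SD 5, shifts of 2, 4 and 6 days give about 9–11%, 22–24% and 42–43% with 30 per arm, and 21–22%, 57–62% and 87–88% with 93 per arm.

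**4. A second set of assumptions.** 103 per arm, 79% suppressed by month 6 and 85% by month 12 in both arms, draw days uniform within ± 7 days (SD 14/√12 = 4.0), SoC later by 3, 5 or 7 days. The draw-date log-rank rejects in 56%, 91% and 99%, or in 32%, 63% and 81% if half are already suppressed at baseline and excluded. The tighter spread of visit days, and the larger numbers when nobody is excluded, push these rates up.

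**5. Missed visits.** Keep the second set, with no timing shift. Suppose the month 6 draw is missed by 21% of SoC (illustrative, from the hospital's 79% retention) and 5% of CFLU (assumed), and everyone attends month 12. The month 6 step is then 0.79 × 0.79 = 62.4% in SoC and 0.79 × 0.95 = 75.1% in CFLU. This gap of 12.6 points has no true difference behind it. The draw-date log-rank rejects in about 23% (15% if half are excluded at baseline). Coding by nominal visit, with the late result simply assigned to month 12, still rejects in about 16% (10%).

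**6. Interval-censored analysis of the same kind of data.** A grouped proportional-hazards likelihood-ratio test, with 0–12 months as the interval when month 6 is missed, rejected in 4–7% in all four null settings run, including a 7-day shift combined with unequal missed visits. With a true difference (79% against 94% at month 6; 85% against 96% at month 12, the latter assumed) and no shift, power was 78% for the draw-date log-rank and 92% for the interval-censored test.

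**The case against.** The plan does not commit the error outright. It never says that the draw date is the event date, and the sentence about extracting visit dates concerns loss to follow-up. It promises curves, not a log-rank test or hazard ratio; the inferential methods it names are chi-square, odds ratios and logistic regression. If curves are only drawn, a shift of 2 to 6 days on a 336-day axis is hardly visible. Reminders may prevent missed visits without moving the in-window date, and participants in both arms get appointment dates and phones. No attendance data are given, and the simulated rates fall steeply as the attendance SD rises. The main virological comparison, the proportion suppressed at each visit, is already planned.

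Most of this stands. It limits the point to an undefined outcome with a foreseeable bad default, and makes the rejection rates conditional. It does not remove the point: once two scheduled samples are put into a survival curve some date must be chosen, and nothing in the plan steers the analyst away from the draw date. Nor is drawing without testing safe, since unequal missed visits change the height of the month 6 step (working, item 5).

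A reader might also infer that time to suppression cannot be estimated at all, or that the curves would measure punctuality alone. Neither is supported. Exact times are unobservable, but a coarse distribution can be estimated from the intervals. Step heights still carry the proportion suppressed, as the 78% power without a timing shift shows. Samples are also not strictly limited to three, because interim repeat draws are allowed.

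**Conclusion.** The point holds in this form: suppression times are observed only within intervals of about 24 weeks, the plan announces ordinary survival curves, and it defines neither an event date nor a method for interval-censored data. With draw dates as event dates, the curves would mix suppression with visit timing and missed visits, both of which the CFLU arm's reminders and tracing may alter.

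The lack of exact times follows from the schedule and is certain. The size of any bias is not. With 50 viraemic participants per arm and a log-rank test that the plan does not state, the false-positive rate runs from about 5–7% (2 days earlier, SD 10) to 60–64% (6 days earlier, SD 5). It rests on assumed shifts, SD, suppression rates and numbers viraemic at entry. The month 6 and month 12 proportions, and the sample size of 206 built on them, are unaffected. This should be corrected before analysis, but it does not threaten the main comparison.

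**What to change.** - Keep the planned proportions below 1000 copies/mL at months 6 and 12, by arm, as the virological result.
- If time to suppression is kept, analyse it as interval-censored between the last unsuppressed and the first suppressed sample, including interim draws, with a Turnbull curve or an interval-censored proportional hazards model. Discrete time by nominal visit (6, 12) is a simpler alternative. It then needs a rule that a participant who missed month 6 and is suppressed at month 12 contributes the whole 0–12 month interval, not an event at month 12.
- Do not treat the draw date as an exact event time.
- State the time origin (randomisation or ART start), how participants already suppressed at baseline are handled, and the rules for missed, out-of-window and interim draws.
- Dropping the time outcome is an option, not a necessity.

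The cost is SAP wording: no added samples, visits or participants. The continuous-looking curves are lost, and the estimate that replaces them is coarse. Interval censoring also assumes that the timing of draws, including interim draws, is unrelated to suppression, so the number of draws and missed visits should be reported by arm.
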